### **Laser settings**

After reaching the renal pelvis with the flexible ureteroscope, the 150µm laser fiber is inserted through the working channel of the scope. The laser is then activated for 120 seconds starting with the lowest settings. Temperature registration is then continued for another 60 seconds. When the temperature in the renal pelvis has returned to basic, the registration is repeated for the next laser settings. A total of 4 series is performed with different laser settings (2.4W, 8W, 20W and 30W) with 150µm laser fiber. Laser activation is immediately paused if the registered temperature reach 43°C. The following laser settings will be used in the study:

**5 watts of power:** 0.5 J / 10 Hz, short pulse

**10 watts of power:** 0.5 J / 20 Hz, short pulse

**20 watts of power:** 0.5 J / 40 Hz, short pulse

**30 watts of power:** 1 J / 30 Hz, short pulse

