#### **Power analysis:**

In the pre-clinical study, we found that the peak temperatures when activating the TFL laser continuously for 180 seconds using a 150 $\mu$ m fiber were 26.7°C, 32.8°C and 45.2°C for the laser settings of 0.4J/6Hz (2.4W), 0.8J/10Hz (8W) and 0.2J/100Hz (20W), respectively . The

corresponding baseline temperature before activating the laser were 24.1°C, 24.5°C and 25.3°C.

We expect both the baseline and the peak temperatures to be approximately similar also during URS in real patients as the temperature of the irrigational fluid is the same as in the pre-clinical study (23 °C) .

Peak temperatures for different laser settings will be compared using paired-samples *t*-test. Using the peak temperatures for the different laser settings found in the pre-clinical study, the sample size can be calculated for the clinical study assuming the peak temperature will be similar. As the peak temperatures for different laser settings will be compared within the same individual, paired samples *t*-test is used. The total number of patients required for comparison is therefore lower than if peak temperatures were measured for only one laser setting in each patient. In that case independent samples *t*-test would have been the correct test for comparison.

The effect size is calculated to be 4.4 comparing peak temperatures at 2.4W and 8W, and 2.9 comparing peak temperatures at 8W and 20W. The assumed peak temperatures for 2.4W, 8W and 20W are 26.7°C, 32.8°C and 45.2°C, respectively. The corresponding standard deviations are assumed to be 0.8, 1.6 and 4.9, respectively. The  $\alpha$  error probability is set to 0.05 and the power (1- $\beta$  error probability) is set to 0.8.

Using G\*Power, version 3.1.9.4 and IBM SPSS Statistics 27 for power analysis, the total sample size is calculated to be 3 when comparing 2.4W and 8W and 4 when comparing 8W and 20W. The highest number of these two calculations is considered appropriate to use. To compensate for possible non-evaluable patients, a total of 10 patients are planned for inclusion in the study.

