### **Statistical analyses:**

Statistical analyses will be performed using IBM SPSS Statistics 27 or higher (IBM, Armonk, NY). A *p*-value < 0.05 will determine statistical significance.

Peak temperatures between different laser settings will be compared using paired-samples *t*-tests. Wilcoxon test for related samples will be used comparing the continuous temperature profiles for different laser settings. Exact  $\chi^2$ -test test and Fisher's Exact test are used comparing categorical variables.

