Laser disintegration of the stone is started using the lowest laser setting of 5W continuously for 120 seconds followed by 60 seconds of idling laser. Temperature measurements are maintained continuously during these 180 seconds, with two measurements per second. When the temperature in the renal pelvis has reached base temperature after one series of measurements, the procedure is repeated for the next laser setting. In total, URS lithotripsy are performed for three different settings. If 43°C is reached during laser activation for any of the laser settings, the laser will be stopped immediately and further laser activation with that specific settings will be aborted. Laser activation with subsequent settings will be ready when base temperature is reached.

If stone treatment is not completed at the end of the three series of laser activation and temperature measurements, further stone disintegration will be performed before finishing the URS procedure. A JJ-stent is placed at the end if deemed necessary by the surgeon. The nephrostomy tube is removed when considered appropriate. If a JJ-stent is placed after the procedure, this is removed according to standard routine after 1-2 weeks in the outpatient clinic. Follow-up with CT is performed at 3 months post endoscopically for all patients to assess stone free status and exclude a ureteral stricture in addition to a clinical consultation.

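### Settings appear to run in ascending order in every patient and raw peaks are compared, so start temperature enters the contrast unadjusted and power cannot be separated from series number

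*Combined protocol and SAP*

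**What the plan says.** **Order.** The URS procedure section states "Laser disintegration of the stone is started using the lowest laser setting of 5W continuously for 120 seconds followed by 60 seconds of idling laser". The Laser settings section agrees on the start ("The laser is then activated for 120 seconds starting with the lowest settings") and continues: "the registration is repeated for the next laser settings". Only the first position is fixed in words. The ascending order of the rest is the natural reading of that phrase and of the list, which runs 5, 10, 20, 30 W. No randomised or counterbalanced order appears.

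**Safeguard.** "When the temperature in the renal pelvis has reached base temperature after one series of measurements, the procedure is repeated for the next laser setting". The Laser settings section repeats the rule in similar terms. Neither section gives a value, a tolerance or a reference point for base temperature.

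**Analysis.** The Statistical analyses section says "Peak temperatures between different laser settings will be compared using paired-samples" t-tests. It has no term for start temperature, series number or stone state.

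**Bench data.** The Power analysis section gives peaks of 26.7, 32.8 and 45.2°C at 2.4, 8 and 20 W, and reports that the "corresponding baseline temperature before activating the laser were 24.1°C, 24.5°C and 25.3°C".

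**Number of series and settings.** The Laser settings section says "A total of 4 series is performed with different laser settings (2.4W, 8W, 20W and 30W) with 150µm laser fiber", but the list beneath it gives 5, 10, 20 and 30 W, and the procedure section speaks of three settings.

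**The concern.** The plan justifies a very small sample by comparing settings within the same patient. The main threat to such a comparison is anything that changes systematically from the first series to the last. If every patient goes through the settings in the same order, such a change falls entirely on the setting contrast, and no model fitted afterwards can remove it.

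Two such changes are plausible here. The start temperature of each series may differ within whatever counts as base. The stone is also progressively consumed, because the same stone is treated through all series.

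The first affects both aims: it can carry into the peak temperature (hypothesis 2), and it moves the time at which 43°C is crossed (hypothesis 3). It can be dealt with in the analysis, because temperature is logged twice per second, but the plan does not do so. The second can only be acknowledged.

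**Working it through.** **1. Reproduce the plan's sample size.** Inputs from the Power analysis section: peaks 26.7, 32.8, 45.2°C; SDs 0.8, 1.6, 4.9; alpha 0.05 (taken as two-sided); power 0.80. The within-patient correlation r is not stated. SD of the difference = √(s₁² + s₂² − 2·r·s₁·s₂). With r = 0.5:

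- 2.4 W vs 8 W: √(0.64 + 2.56 − 1.28) = 1.386; effect size 6.1/1.386 = 4.40; n = 3 (power 0.944).
- 8 W vs 20 W: √(2.56 + 24.01 − 7.84) = 4.328; effect size 12.4/4.328 = 2.87; n = 4 (power 0.954).

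The plan states 4.4 and 2.9, with n = 3 and 4. These reproduce, which supports r = 0.5 as the value used.

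**2. Can power be separated from series number?** Take 10 patients and four series. A model with patient and series effects has rank 10 + 3 = 13. In one fixed order, adding setting effects leaves the rank at 13, so no setting contrast is estimable apart from series. With three series the rank is 12 before and after. (With balanced orders it would rise from 13 to 16, or from 12 to 14; this only illustrates the aliasing.)

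**3. Size of a start-temperature effect.** Bench start temperatures differ by 24.5 − 24.1 = 0.4°C and 25.3 − 24.5 = 0.8°C. Assume that shifts of this size occur between series in patients, that they add one-for-one to the peak, and that power has no effect. The rejection rate of the two-sided paired t-test at n = 10 (noncentral t, noncentrality √10 × shift/SD), with each shift matched to its own step, is:

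| Step | Shift (°C) | SD of difference (r = 0.5) | Rejection rate | Range for r = 0 to 0.7 |
|---|---|---|---|---|
| 2.4 W vs 8 W | 0.4 | 1.386 | 13% | 10% to 16% |
| 8 W vs 20 W | 0.8 | 4.328 | 8% | 7% to 9% |

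**4. Compared with the expected effect.** 0.4/6.1 = 6.6% and 0.8/12.4 = 6.5%. Shifts of this size would bias the estimated differences slightly. They could not produce the expected differences.

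**5. Time to 43°C.** The Background gives about 40 to 45 s at 20 W on the bench. As an illustration, take 45 s from a start of 25.3°C.

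- Linear heating: (43 − 25.3)/45 = 0.393°C per second, so a 0.8°C shift in the start moves the crossing by 0.8/0.393 ≈ 2 s, to 47 or 43 s.
- First-order heating with a total rise of 45.2 − 25.3 = 19.9°C and the whole curve shifting with its start: time constant 45/ln(19.9/2.2) = 20.4 s. The crossing moves to 20.4 × ln(19.9/1.4) ≈ 54 s for a start 0.8°C lower, and to 20.4 × ln(19.9/3.0) ≈ 39 s for a start 0.8°C higher.

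The heating model is an assumption. The answer runs from about 2 s to about 9 s.

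**6. Stone consumption.** If series run the full 120 s at the listed powers, 5 × 120 + 10 × 120 = 600 + 1200 = 1800 J precede the 20 W series. Before 30 W the total is 1800 + 20 × 120 = 4200 J. If 20 W is stopped at 43°C after about 45 s, as on the bench, it is nearer 1800 + 20 × 45 = 2700 J. The documents give no link from joules or stone size to temperature, so this shows that stone state differs between series, not by how many degrees.

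**7. Does analysing the rise cost power?** Bench rises are 2.6, 8.3 and 19.9°C, so the differences become 5.7 and 11.6°C. With the same SDs (assumed), effect sizes are 5.7/1.386 = 4.11 and 11.6/4.328 = 2.68, and n stays 3 and 4.

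**The case against.** **The plan already guards against this.** It does in part. The return-to-base rule targets both residual heat and start-temperature drift, and any account of this point must include it. What remains is narrower: base is undefined, and the analysis does not use the start temperature actually recorded. The rule does nothing about the stone.

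**The drift is assumed.** This stands. The bench start temperatures are reported by setting; nothing says those runs were sequential or that the differences reflect order. The rates in the table are illustrations. So is the one-for-one carry-over: if the pelvis comes close to a thermal equilibrium during activation, less of a start difference would reach the peak. Equally, the Background says no clinical intrarenal temperature data exist, so nothing in the documents bounds the shift in patients.

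**A reader might infer that the comparison is uninterpretable, or that the false-positive rate reaches 37%.** The documents support neither. The 37% arises only when the 0.8°C shift of the 8 W to 20 W step is combined with the SD of 1.39 from the 2.4 W to 8 W step; matched to its own SD, that shift gives 8%. Biases near 6.5% of the expected effect do not make large contrasts uninterpretable.

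**A reader might also infer that the order should be randomised, at least among low settings.** That does not follow either. Starting low may be a precaution, although the documents do not say so. The bench margins are for 2.4 and 8 W, not the listed 5 and 10 W, so they do not settle which settings are interchangeable in patients. Reordering only low settings would leave the 20 W and 30 W contrasts confounded. It would also estimate a series effect with a standard error of about 1.39/√10 = 0.44°C, a 95% interval of about ±1.0°C, which is too wide to detect shifts of 0.4 to 0.8°C.

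**Conclusion.** The point holds in a limited form. On the natural reading of the order, power is fully aliased with series number and stone state, and the planned paired tests on raw peaks ignore the start temperature of each series. The likely size is modest: under the stated assumptions, false-positive rates of about 13% and 8% instead of 5% if power had no effect, and about 6.5% bias against the expected differences. It matters more if clinical differences prove smaller than on the bench, and for the time to 43°C. The conclusion rests on ascending order beyond the first setting, shifts of bench size, additive carry-over and r near 0.5. The effect of stone state on temperature cannot be sized from the documents.

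**What to change.** With the order of settings unchanged:

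1. In Statistical analyses, compare settings on the rise from each series' own recorded start temperature (or adjust for it), alongside the absolute peak. Flag any series stopped at 43°C, since its peak and its rise are cut short by the stop.
2. Account for start temperature in the comparison of time to 43°C.
3. State what counts as base temperature for measurement purposes, including the tolerance applied, so that the start value is defined.
4. Word the conclusions as the effect of each setting as given in ascending order, and list series number and stone state as limits that cannot be separated from power.
5. Reconcile the passages that conflict on the number of series (three vs four) and on the settings (2.4, 8, 20, 30 W vs 5, 10, 20, 30 W).

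The cost is a few sentences. The data are already recorded twice per second, no patients or procedures are added, and on the bench figures the required n does not change. Whether any settings may be reordered is for the clinical team, and no change is proposed here.

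### The protocol gives three or four laser series at two different sets of powers, and its power calculation describes other pulse settings and a longer laser-on time

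*Combined protocol and SAP*

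**What the plan says.** All references are to the combined protocol and SAP.

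- **Laser settings, running text:** "A total of 4 series is performed with different laser settings (2.4W, 8W, 20W and 30W").
- **Laser settings, list:** introduced by "The following laser settings will be used in the study", it gives 5 W ("0.5 J / 10 Hz, short pulse"), 10 W (0.5 J/20 Hz), 20 W ("0.5 J / 40 Hz, short pulse") and 30 W (1 J/30 Hz). On duration the section says "The laser is then activated for 120 seconds starting with the lowest settings".
- **The URS procedure and follow-up:** "Laser disintegration of the stone is started using the lowest laser setting of 5W continuously for 120 seconds". It then says "In total, URS lithotripsy are performed for three different settings", and later refers to treatment not completed "at the end of the three series of laser activation and temperature measurements".
- **Power analysis:** mean peaks of 26.7, 32.8 and 45.2°C (SD 0.8, 1.6 and 4.9) at 2.4, 8 and 20 W, taken from a bench study with 180 s of continuous activation. The effect sizes are 4.4 and 2.9, giving 3 and 4 patients; 10 are planned.
- **Statistical analyses:** paired t-tests of peak temperature between settings. No pairs are named.
- **The 43°C stop** appears in the ethics, procedure and Laser settings sections. Laser settings speaks of pausing; the procedure section speaks of aborting that setting.

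**The concern.** Laser setting is the within-patient factor, and comparing peak temperature between settings is the main aim. A reader cannot tell whether a patient has three series or four. Nor can a reader tell whether 30 W is among them, the one listed setting above the 20 W that the Background expects to be safe. Two operators following the text could deliver different series.

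Because no pairs are named, three settings allow C(3,2) = 3 comparisons and four allow C(4,2) = 6. The primary comparison could then be settled after the data are seen.

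The sample-size calculation does not help, because it describes other conditions and ignores the stop at 43°C. If 20 vs 30 W is one of the comparisons, the stop limits the difference in peaks that can be observed. A non-significant result there would not be evidence of equal heating.

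**Working it through.** **1. The passages side by side**

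| Source | Series | Powers | Laser-on time |
|---|---|---|---|
| Laser settings, text | 4 | 2.4, 8, 20, 30 W | 120 s |
| Laser settings, list | 4 listed | 5, 10, 20, 30 W | (as above) |
| URS procedure | 3 (said twice) | starts at 5 W | 120 s |
| Power analysis (bench) | 3 | 2.4, 8, 20 W | 180 s |

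Rounding does not explain the difference. Every energy × frequency product equals its stated power:

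- List: 0.5×10 = 5, 0.5×20 = 10, 0.5×40 = 20, 1×30 = 30.
- Bench: 0.4×6 = 2.4, 0.8×10 = 8, 0.2×100 = 20.

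No listed pulse setting equals a bench setting; even the shared 20 W differs (0.5 J/40 Hz against 0.2 J/100 Hz). With 5 W first, three sets of three fit the list: 5/10/20, 5/10/30 and 5/20/30 W.

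**2. The plan's own figures**

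dz = (m2 − m1)/√(s1² + s2² − 2r·s1·s2), two-sided paired t-test, alpha 0.05.

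- 2.4 vs 8 W, r = 0.5: 6.1/√(0.64 + 2.56 − 1.28) = 6.1/1.386 = 4.40; n = 3 gives power 0.944.
- 8 vs 20 W, r = 0.5: 12.4/√(2.56 + 24.01 − 7.84) = 12.4/4.328 = 2.87; n = 4 gives power 0.954.
- At r = 0, dz is 3.41 (n = 3, power 0.827) and 2.41 (n = 4, power 0.878).

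The stated 4.4 and 2.9, and n of 3 and 4, therefore reproduce at r = 0.5 with a two-sided test. The plan states neither the correlation nor the sidedness.

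**3. The stop at 43°C**

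On the plan's 20 W mean and SD, assuming normality, P(peak ≥ 43°C) = 1 − Φ((43 − 45.2)/4.9) = 0.673. The Background reports that 43°C was reached on the bench at 20 W after about 40–45 s, depending on fibre size, which is well within 120 s. The assumed 12.4°C difference between 8 and 20 W could not be fully observed.

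**4. What the listed settings might need**

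Assumption: means and SDs linear in watts between the 180 s bench values. This gives 5 W = 29.5°C (SD 1.17) and 10 W = 34.9°C (SD 2.15).

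| Pair | dz at r = 0, 0.5, 0.7 | n for 80% power |
|---|---|---|
| 5 vs 10 W | 2.18, 2.86, 3.40 | 4, 4, 3 |
| 10 vs 20 W | 1.93, 2.43, 2.77 | 5, 4, 4 |

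At n = 10 and r = 0, with peaks capped at 43°C, simulated power is 1.000 and 0.999. With uncapped differences 25% smaller, it is 0.995 and 0.982 at r = 0. If the differences were halved, it is 0.865 and 0.775 at r = 0, and 0.98 and 0.926 at r = 0.5.

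**5. 20 vs 30 W, illustration only**

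The documents give no 30 W value and no figure for overshoot after the stop. Assumptions: 30 W mean extrapolated to 45.2 + (10/12)×12.4 = 55.5°C, SD 7.65 (extrapolated) or 4.9, r from 0 to 0.7, overshoot SD 0.3°C, n = 10.

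- Every stopped series peaks at exactly 43°C: power 9–13%.
- Equal overshoot at both settings (0.2 to 1.0°C): 12–22%.
- Larger overshoot at 30 W (0.2/0.5 to 1.0/2.0°C): 31–97%.
- Exact cap with the 20 W mean at 43 or 40°C and 30 W 10.3°C higher: 30–46% or 58–91%.
- No cap, SD 7.65: 0.891, 0.990 and 0.999 at r = 0, 0.5 and 0.7.

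The size depends almost wholly on the assumptions; the direction does not, since a common stop compresses this contrast. For 10 vs 30 W, capped power stays above 0.999.

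**The case against.** The list carries full pulse parameters and agrees with the 5 W start in the procedure section. The 2.4 and 8 W in the running text may simply be carried over from the bench study. On that reading only the count of three is out of line, and no passage suggests dropping 10 or 20 W. This is a reasonable guess, but no passage confirms it, and it leaves three against four, and therefore 30 W, unsettled.

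The power analysis says openly that it assumes clinical peaks similar to the bench. The bench powers bracket 5 and 10 W, and restating the calculation is unlikely to change n. That stands: on its own this would be a documentation gap. At r = 0.5 the interpolated 10 vs 20 W comparison needs 4 patients, the same as the plan's 8 vs 20 W. The gap between 180 s and 120 s also matters less at 20 W, where the stop would often end activation earlier.

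Finally, the hypotheses contrast high with low settings, no passage singles out 20 vs 30 W, and time to 43°C, already the secondary aim, would inform that comparison. This also stands, and is why the 30 W figures are an illustration and not a reason for the correction.

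**Conclusion.** The concern holds. The contradiction in the number of series and the powers is plain in the text and nothing else in the document resolves it, so the factor behind the main aim cannot be carried out as written. It must be corrected.

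The stated sample sizes are arithmetically right at r = 0.5 but do not describe the planned comparisons. They use other pulse settings, 180 s instead of 120 s, nothing for 5, 10 or 30 W, and a 20 W mean above the plan's own stop.

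Ten patients are not shown to be too few. On linear interpolation of the bench figures, 3 to 5 patients suffice for 5 vs 10 W and 10 vs 20 W. Only with halved differences and r = 0 does 10 vs 20 W fall just below 80% power at n = 10 (0.775). Confidence is high for the text conflict and does not extend to the 20 vs 30 W illustration.

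**What to change.** The sponsor should:

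1. Reconcile Power analysis, The URS procedure and follow-up, and Laser settings into one set of settings (J, Hz and W) and one number of series, and say whether 30 W is run. Which is right is for the sponsor.
2. Align the pausing and aborting wording at 43°C across the two sections.
3. Name in Statistical analyses the pairs to be compared on peak temperature.
4. Restate Power analysis for those pairs at 120 s, allowing for the 43°C stop, with the sidedness, the assumed correlation and a range (for example r = 0 to 0.7). State that no power basis is given for any 30 W comparison.
5. If 20 vs 30 W is among the pairs, add: *The 43°C stop limits the difference in peak temperature between 20 W and 30 W. A non-significant difference is not evidence of equal heating and is read together with time to 43°C.*

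The cost is protocol wording and a rerun calculation; no change in n is shown to be needed. At r = 0 the stated figures become slightly less favourable (10 vs 20 W needs 5 on the interpolated values, where 8 vs 20 W needs 4). The plan must also say openly that 30 W has no power basis.

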### **Study progress**

The date for completing the data registration form, patient information and consent form, and application for approval by The National Committees for Research Ethics in Norway is set to November 1st 2022.

After achieving ethical approval, application for approval from The Data Protection Authorities at HUH will be sent. Prior to enrollment, the study also needs to be registered in the clinical research database for randomized trials, ClinicalTrials.gov.

Inclusion of patients and ureteroscopies are expected to start in January 2023, and the inclusion is expected to close during June 2023.

Data analyses and writing a draft is set to autumn/winter 2023. Final manuscript ready for submission is planned during January 2024.

